3.2.7. Stratification, Subsets, and Covariates

Eligible Patients will be stratified on Screening serum IGF-1 level (> 2.5 ULN vs. ≤ 2.5 ULN age and sex adjusted by the central lab).

The following covariates may be used for further exploration in subgroups or as covariates:

- Age group (< 65 years vs. ≥ 65 years)
- Race (Caucasian vs non-Caucasian)
- Gender
- Serum IGF-1 level status (>2.5 ULN vs. ≤ 2.5 ULN)

Additional baseline demographic and disease characteristics may also be considered as covariates.

3.3. Primary Analysis

3.3.1. Primary Endpoint Definition

The primary endpoint is percent change from Baseline to Week 27 in IGF-1 within each ISIS 766720 treated group and overall.

3.3.2. Analysis of Primary Endpoint

The analysis of the study primary endpoint will be conducted in the PPS. The results will be summarized by the ISIS 766720 dose received at randomization and overall. In addition, because most of patients will have dose escalation after primary endpoint of Week 27, the results will also be summarized by the maximum ISIS 766720 dose received through the study and overall.

Subset analysis will be conducted among uncontrolled population ($IGF-1 > 1.3 \times ULN$ at Day 1) and high-strata IGF-1 population ($IGF-1 > 2.5 \times ULN$ at Screening), separately. The data will be analyzed using one-sample t-test to detect the reduction of IGF-1 significant different than zero at Week 27. The normality assumption for one-sample t-test model will be assessed by the Shapiro-Wilk test. In the case of data departs substantially from normality, the nonparametric Wilcoxon signed rank test will be applied instead. Additional summary in FAS will be provided.

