6.1.2. Treatment Period

During the 1.5-year study, each patient will receive up to 20 SC doses of ISIS 766720 with a planned monthly interval between each dose except for a booster dose at Day 15 (WK 3). All patients will have bi-weekly visits beginning at Day 1 (WK 1) through Day 113 (WK 17). After that visits occur monthly through Day 505 (WK 73) with an additional visit on Day 183 (WK 27) for primary endpoint assessments. Of the 24 required study visits, 14 selected study visits may be performed outside of the clinic by a Sponsor selected Home Health Care professional (See [Appendix A](#)). Home health visits are optional and would be arranged by study center staff if requested by the patient. In consultation with the Sponsor, a Home Health Care visit may be conducted for a study visit day that was intended to be an in-clinic visit. It is preferable that the entire visit is conducted, however the following assessments may be omitted: ECG, body weight, physical exam, ring size, and OGTT. If a visit cannot be performed in the clinic or by Home Health, patient contact (e.g., phone, text, email or video) is required by site personnel to assess any adverse events or changes in concomitant medications. Any assessments not completed at the Home Health Care visit should be attempted at the next clinic visit.

Safety, efficacy, PK and exploratory assessments will be performed per [Appendix A](#), [Appendix B](#), and [Appendix C](#) throughout the Treatment Period on ISIS 766720 administration days. At each visit, patients should arrive fasting at least 8 hours for safety and clinical laboratory evaluations; vital signs, blood pressure (BP) assessments, AEs and concomitant medication usage will be assessed during each visit.

A 2-hour OGTT and GH response procedure will be conducted pre-dose on Day 1 and pre-dose on Day 183 (WK 27) and Day 505 (WK 73). The pre-dose-Day 1 OGTT and GH response procedure may be conducted between Day -41 and pre-dose Day 1. To decrease the study burden on potential patients, it is suggested that this procedure is done after the patient has completed and qualified based on all other screening procedures. The OGTT and GH Response procedure can be conducted in the clinic or as arranged by a Home Health Care professional. The patient must fast 10-hours prior to OGTT and GH Response assessment.

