8.7. Adjustment of Dose and/or Treatment Schedule

ISIS 766720 dose adjustments and interruptions will be allowed for safety, tolerability or efficacy. Dose adjustments for efficacy (no higher than a 200 mg dose) may be made after Week 17 IGF-1 results are available. It is recommended to maintain an adjusted dose for efficacy for 3 months prior to further adjustment. Any dose adjustment requires consultation with the Sponsor Medical Monitor or Designee.

Patients may have their dose interrupted in response to AEs after consultation with Sponsor Medical Monitor or Designee.

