10.3. Populations

Safety Set: All patients who are randomized and receive at least 1 dose of ISIS 766720.

Full Analysis Set (FAS): All randomized patients who receive at least 1 dose of ISIS 766720 and have at least 1 post-baseline efficacy or PD assessment.

Per Protocol Set (PPS): All FAS patients who complete at least 6 of the 8 doses of ISIS 766720 with the first 27 Weeks administered and have no significant protocol deviations that would be expected to impact efficacy.

PK Set: All patients who are randomized and receive at least 1 dose of ISIS 766720 and have at least 1 evaluable PK sample.

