⁵ IGF-1 results will be available from Week 17 visit and every three months or more frequently per PI judgement in consultation with Sponsor Medical Monitor or Designee

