3.4.2. Analysis of Secondary Endpoints

The analysis population will be conducted in both FAS and PPS. The results will be summarized by the ISIS 766720 dose received at randomization and overall. In addition, the results will also be summarized by the maximum ISIS 766720 dose received through the study and overall.

Subset analysis will be conducted among uncontrolled population ($IGF-1 > 1.3 \times ULN$ at Day 1) and high-strata IGF-1 population ($IGF-1 > 2.5 \times ULN$ at Screening), separately.

Proportion of subject incidence of achieving within 1.2 times, achieving 1.0 times of ULN over time will be summarized at each scheduled visit respectively. The estimated proportion with 95% confidence interval will be provided.

Absolute, change and percent change from Baseline to each scheduled post-baseline visit in IGF-1 over time will be summarized at each scheduled visit.

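### Grouping Week 27 IGF-1 results by the highest dose received in the whole study credits them to doses largely not yet given, and the groups can be selected on response

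*Combined protocol and SAP*

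**What the plan says.** SAP 3.3 covers one endpoint, the percent change in serum IGF-1 from Baseline to Week 27. Section 3.3.2 first summarises it by randomised dose and overall. It then commits to a second grouping: "the results will also be summarized by the maximum ISIS 766720 dose received through the study and overall". The reason given is "because most of patients will have dose escalation after primary endpoint of Week 27".

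SAP 3.4.2 repeats this for the secondary endpoints: "In addition, the results will also be summarized by the maximum ISIS 766720 dose received through the study and overall". Those endpoints include normalisation to within 1.2 and 1.0 times the limits at Day 183 (Week 27), as well as IGF-1 over time.

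Protocol 8.7 governs dose changes: "Dose adjustments for efficacy (no higher than a 200 mg dose) may be made after Week 17 IGF-1 results are available". It allows for more than one change ("It is recommended to maintain an adjusted dose for efficacy for 3 months prior to further adjustment") and gives no step size. Footnote 5 of Appendix B says that "IGF-1 results will be available from Week 17 visit and every three months or more frequently per PI judgement".

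SAP 3.1 allows a further summary by adjusted dose but does not say at which visit the dose is taken. No visible text limits the maximum-dose grouping to later visits or cautions on how to read it. SAP 3.5 is not visible and 3.1 is partly redacted.

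**The concern.** There are two separate faults.

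- **Timing.** A dose first given after Week 27 cannot have affected a Week 27 value. If most escalation comes later, a patient who was on 120 mg at Week 27 can appear in the 160 or 200 mg row.
- **Selection.** The trial is open label, IGF-1 results are released from Week 17, and dose may be raised for efficacy. The maximum dose can therefore be a consequence of the response it is used to group. If poor responders are escalated, the lower rows keep the better responders.

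A table with dose rows invites a dose-response reading. The 200 mg row would show results from patients largely still on a lower dose, and the 160 mg row could mix patients randomised to 120 and 160 mg. SAP 3.3.4 allows additional summaries for publication or regulatory interaction, so such a table could travel beyond the study report.

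**Working it through.** Changes are percent change in IGF-1; more negative means a larger reduction.

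**1. The plan's own figure.** SAP 3.3.3 assumes a 27.5% reduction with SD 30% and 12 evaluable patients per group. The noncentrality is (27.5/30) × √12 = 3.18. With 11 degrees of freedom and two-sided 5%, exact power is 82.4%; with 11 patients it is 78.2%. So 12 is the smallest group size reaching 80%, and 36/0.9 = 40. The sample size reproduces and this point does not change it.

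**2. Timing.** Protocol 6.1.2: "each patient will receive up to 20 SC doses of ISIS 766720 with a planned monthly interval between each dose". Protocol 10.3 defines the per protocol set by patients who "complete at least 6 of the 8 doses of ISIS 766720 with the first 27 Weeks administered". The schedule agrees:
- Before Week 27: Days 1, 15, 29, 57, 85, 113, 141, 169 = 8 doses.
- After: Days 197 to 505 every 28 days = (505 − 197)/28 + 1 = 12 doses.

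Only the Week 21 and Week 25 doses fall between the Week 17 visit and Week 27. At most 2 of the 8 could therefore be efficacy-adjusted.

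**3. Mislabelling without selection.** Assumptions: only the 120 and 160 mg arms, 1:1; true changes -22.5 and -32.5, whose average is the SAP's -27.5; 70% of each arm escalated after Week 27 regardless of response; 200 mg cap from protocol 8.7. Each row is a weighted mean of the arms that feed it.

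| Step pattern | 120 row | 160 row | 200 row |
|---|---|---|---|
| One 40 mg step | -22.5 | 0.7(-22.5) + 0.3(-32.5) = -25.5 | -32.5 |
| 120 goes to 160 or 200 equally | -22.5 | [0.35(-22.5) + 0.30(-32.5)]/0.65 = -27.1 | [0.35(-22.5) + 0.70(-32.5)]/1.05 = -29.2 |
| All straight to 200 | -22.5 | -32.5 | [0.7(-22.5) + 0.7(-32.5)]/1.4 = -27.5 |

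In the first pattern the 200 mg row is simply the Week 27 effect of 160 mg. In the third, the 200 mg row looks weaker than the 160 mg row although nobody had yet received 200 mg. If both true changes are -27.5, every row reads -27.5.

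**4. Selection with no dose effect, closed form.** All groups have mean -27.5 and SD 30. A fraction p with the poorest marker values is escalated, and the marker has correlation r with the Week 27 change. With c = Φ⁻¹(1 − p):
- escalated mean = -27.5 + 30·r·φ(c)/p
- non-escalated mean = -27.5 − 30·r·φ(c)/(1 − p)

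For p = 0.6 and r = 0.5, φ(c) = 0.386, giving -17.8 and -42.0, a spurious gap of 24.1 points. Over p = 0.60 to 0.75 and r = 0.5 to 0.7 the gap is about 24 to 36 points. At r = 0 it is zero.

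**5. Selection with a softer rule, by simulation.** One million patients per scenario, with all escalation after Week 27. Baseline is lognormal with median 2.0 × ULN and log-SD 0.4, clipped to 1.3–5. The probability of escalation when a guiding IGF-1 is above/below ULN is 85%/20%, 90%/50%, 70%/30%, 70%/50% or 70%/70%. The correlation of the guiding value with the Week 27 change is 1, 0.7 or 0.4. The 70%/70% case counts once, giving 13 scenarios for each of the three step patterns, 39 in all; 59–79% of patients escalate.

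- *No dose effect, with selection:* the 120 mg row reads -29.4 to -44.6 and the 200 mg row -19.2 to -26.5. Normalisation (≤ 1.0 × ULN) is 31–66% against 8–25%; by randomised dose it is 27%. A weaker case (70%/30%, correlation 0.4, one step) gives -30.9 against -25.2.
- *Graded effect (-22.5/-32.5), all 13 scenarios per pattern:* the true 160-minus-120 gap is -10 points. It reads -3.1 to +13.7 with one step, -4.6 to +9.5 with split steps, and about -10 when all go straight to 200 mg. The sign reverses in 14 of the 39 scenarios: 9 one-step, 5 split, none straight.

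**6. Row size.** Amendment 3 foresees about 30 randomised if the 80 mg group is not run. With 10% drop-out, 30 × 0.9 = 27 are evaluable. The 120 mg row holds about 10–20% of them, or 3 to 5 patients, with a standard error of 30/√5 = 13 to 30/√3 = 17 points.

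**The case against.** The strongest reply is that no planned inference is touched. The randomised-dose summary comes first, the protocol's hypothesis is a within-group test against zero, between-group comparison is optional, and nothing visible plans a dose-response conclusion from maximum dose. That stands, and it limits the weight of the point. It does not make the table correct: the SAP makes it mandatory and attaches no caution.

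Second, the 8-of-20 count does not by itself show when the maximum is reached, because that depends on when escalation happens and protocol 8.7 permits it before Week 27. This is fair. The timing argument rests on the SAP's own statement that most escalation follows Week 27.

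Third, selection is possible but not shown. No numeric escalation rule is given, safety and tolerability changes are also allowed, and the simulation inputs are assumed. Placing all escalation after Week 27 also maximises the mislabelling. The largest normalisation contrasts arise when the guiding value and the outcome are the same IGF-1 result cut at the same limit. All this stands, so the figures are scenario ranges, not forecasts. Many of the shifts are also smaller than the standard error of a 3-to-5-patient row. That imprecision is no defence, since a row that small is a poor basis for any dose statement.

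Fourth, the grouping may have been meant for later visits, and SAP 3.5 is not visible. But 3.3 has no later visit, and the sentences in 3.3.2 and 3.4.2 are visible and unrestricted.

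**Conclusion.** The concern holds. As written, SAP 3.3.2 and 3.4.2 require Week 27 results by a dose that, on the SAP's own account, most patients reach only afterwards and that can depend on their response.

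The mislabelling needs only late escalation. Distortion of the row means needs either a true dose effect or response-related escalation; with neither, all rows read about -27.5. Reversal of the 160 mg against 120 mg ordering needs response-related escalation and depends on the step pattern. The sizes rest on assumed escalation rates, step patterns, correlations, baseline distribution and a two-arm trial.

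The randomised-dose summaries and tests, the overall row and the sample size are unaffected. This should be corrected, but the harm is confined to a supplementary table.

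**What to change.** - In SAP 3.3.2 and 3.4.2, drop the maximum-dose grouping for Week 27 results and report them by randomised dose and overall.
- For later visits, base any summary by dose received, including the adjusted-dose summary in 3.1, on the dose in effect at or before that visit. Label it descriptive and not dose-response evidence, because selection on response remains there.
- Give the same label to any Week 27 summary by dose in effect.
- Report by randomised arm how many patients had a dose change before Week 27, since protocol 8.7 allows efficacy changes once Week 17 results are available.

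The cost is SAP wording, one set of Week 27 tables dropped, one dose-in-effect derivation and one count by arm, all from data already collected.

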3.3.3. Sample Size Consideration

Approximately 40 patients are planned to be randomized in the study while considering an estimated 10% overall drop-out rate. Based on the assumption of expected IGF-1 reduction of 27.5% from Baseline with SD of 30% per treatment group, the minimum sample size of 12 evaluable patients per treatment group will provide 80% power to detect the difference between the null hypothesis of no change and the expected reduction using a 2-sided one-sample t-test with a significant level of 5%.

3.3.4. Planned Interim Analysis

An interim analysis may be conducted when approximately 50% patients complete the primary efficacy endpoint assessment. Additional summaries may be performed to coincide with study milestones, like publication or regulatory interaction.

3.3.5. Incomplete or Missing Data

In general, missing IGF-1 for a scheduled assessment will not be imputed. Patients with missing data for a scheduled assessment time point will be excluded from the summary for that time point.

3.4. Secondary Analyses

3.4.1. Secondary Endpoint Definitions

Normalized IGF-1 level is defined as the ratio of the serum IGF-1 level and patient's upper limit of normal (ULN). The ULN will be varied among patients due to gender and age. Patients whose calculated ratios at scheduled visits are less than or equal to 1.2 or 1.0 will be deemed as achieving normalized IGF-1 at that scheduled visit.

For change from Baseline, non-missing IGF-1 measures over time will be compared to their baseline.

Patients without IGF-1 measure at a scheduled visit will not be imputed for that scheduled visit.

3.4.2. Analysis of Secondary Endpoints

The analysis population will be conducted in both FAS and PPS. The results will be summarized by the ISIS 766720 dose received at randomization and overall. In addition, the results will also be summarized by the maximum ISIS 766720 dose received through the study and overall.

Subset analysis will be conducted among uncontrolled population ($IGF-1 > 1.3 \times ULN$ at Day 1) and high-strata IGF-1 population ($IGF-1 > 2.5 \times ULN$ at Screening), separately.

Proportion of subject incidence of achieving within 1.2 times, achieving 1.0 times of ULN over time will be summarized at each scheduled visit respectively. The estimated proportion with 95% confidence interval will be provided.

Absolute, change and percent change from Baseline to each scheduled post-baseline visit in IGF-1 over time will be summarized at each scheduled visit.

3.6. Pharmacokinetic Analysis

3.6.1. Plasma Concentration Data of Total Full-Length Oligonucleotides

Pharmacokinetic (PK) analysis will be conducted in the PK Population. For all patients, plasma concentrations of ISIS 766720 (total full-length ASO, reported as ISIS 766720-eq.), along with the scheduled (nominal) and actual samples times (i.e., time from SC dosing) and actual dose will be listed (when applicable) for each patient by dose cohort, nominal dose, patient ID, patient immunogenicity (IM) status, IM onset (if applicable) as defined in Section 3.6.4, and day. In addition, percent differences between scheduled and actual sampling times will be listed for all patients. Percent differences between actual administered dose and nominal dose will also be listed.

Plasma concentrations below the lower limit of quantification (LLOQ) will be presented as “BLQ”. For the purpose of calculating descriptive statistics (n, mean, SD, SE, %CV, geometric mean, geometric %CV, median, minimum, and maximum) for plasma concentrations, all BLQ values will be set to zero. Mean plasma concentrations that are BLQ will be presented as BLQ, and the SD, SE, %CV, geometric mean, and geometric %CV will be reported as not applicable. Summary statistics of ISIS 766720-eq. plasma concentrations will be tabulated by nominal dose, nominal day, and scheduled time point.

ISIS 766720-eq. plasma trough (pre-dose) and post-treatment concentration versus time (actual) for each individual patient, as well as the mean (\pm SD or SE) and/or median plasma trough concentrations over time (scheduled), will be presented graphically on linear and semilogarithmic scales without and with stratification by patient immunogenicity status as applicable (see Section 3.6.4).

At the discretion of the pharmacokineticist and/or biostatistician, samples may be excluded from the summary descriptive statistics and mean and median plots if there are large deviations between scheduled and actual sampling times, or large deviations between actual dose and nominal dose.

3.6.2. Plasma Pharmacokinetic Parameters

Non-compartmental pharmacokinetic analysis of ISIS 766720-eq. will be carried out on each individual patient data set where post-treatment profiles are collected using Phoenix WinNonlin Version 8.0 or higher (Pharsight Corporation, Mountain View, CA). Plasma pharmacokinetic parameters in each patient (when applicable) will be determined. For calculation of PK parameters, all BLQ values will be set to zero. The following plasma PK parameters will be calculated (when applicable and not necessarily limited to) based on actual sampling times:

1. C_{\max} : the maximum observed ISIS 766720 concentration in plasma will be determined on Nominal Day 1 and Nominal Day 113.
2. T_{\max} : the time at which C_{\max} occurs will be determined on Nominal Day 1 and Nominal Day 113.
3. $t_{1/2\lambda_z}$: apparent terminal elimination half-life will be calculated from the equation, $t_{1/2\lambda_z} = 0.693/\lambda_z$, where λ_z is the rate constant associated with the apparent terminal elimination phase. A minimum of three data points in the elimination phase will be used to define λ_z and the correlation of determination values (r^2 adjusted) has to be at or greater than 0.8 for the estimate to be accepted. This parameter may be calculated following the last dose if applicable.

Plasma pharmacokinetic parameters will be summarized using descriptive statistics (n, mean, SD, %CV, geometric mean, geometric %CV, median, minimum, and maximum) by nominal dose and day.

3.6.3. Pharmacokinetic/Pharmacodynamic Exposure-Response Analysis

Exposure-response correlations may be explored graphically between plasma exposure (i.e., C_{trough}) and selected PD measures (e.g., serum IGF-1, GH, and GHBP levels) if applicable.

Population PK and PKPD analysis may be performed using the PK and PD data from this study and/or combined with other ISIS 766720 clinical PK data later in the development timeline.

3.6.4. Immunogenicity (IM) Analysis

Immunogenicity (IM) analyses will be conducted in the ‘Safety Set’. Samples collected for IM assessment at selected time points will be analyzed for anti-ISIS 766720 antibodies (i.e., anti-drug antibodies; ADA). Samples will be designated ‘IM positive’ based on both positive screening and confirmation assay results (i.e., confirmed positive result), otherwise they will be deemed ‘IM negative’. Study subjects will be given ‘positive’ subject IM status if they have at least one confirmed positive sample at any time during the Treatment or Post-treatment Evaluation Periods. Study subjects will be given ‘negative’ subject IM status if all evaluated IM sample results during the Treatment and Post-treatment Evaluation Periods are negative and they have at least one evaluable IM result post-dose. Otherwise, study subjects will be given ‘unknown’ subject IM status.

Sample IM status (screen positive/negative, confirmed positive/negative or not evaluable, and when applicable, titer of anti-ISIS 766720 antibodies) before, during, and after treatment with ISIS 766720 will be listed by the ISIS 766720 dose received (80 mg, 120 mg or 160 mg). Subject IM status (positive/negative or unknown) for all evaluable patients, along with the study day associated with the first positive IM status emerged (T_{first} , i.e., onset of ADA development), the last positive IM status observed (T_{last}) and max and/or end of treatment titer will be listed by treatment and dose.

Additionally, the sample and patient IM incidence (number) and incidence rate (percent) will be summarized as the total number and percent of evaluated patients with antibody negative, positive, and unknown status by the ISIS 766720 dose received (80 mg, 120 mg or 160 mg). Furthermore, onset, and peak titer of the ADA response, if applicable, will be summarized as median, interquartile range (25th percentile, 75th percentile), and range (minimum, maximum).

Other immunogenicity data analysis may be conducted at the discretion of the pharmacokineticist and/or statistician. Potential relationships between immunogenicity results (e.g., IM status) and selected efficacy (e.g., %change in serum IGF-1, GH, and GHBP levels), safety, and pharmacokinetic measures (e.g., C_{trough}) may be evaluated in an exploratory manner either in this report and/or combined with other ISIS 766720 clinical PK data later in the development timeline.

